10.4. Vital Signs

The results and change from Baseline to each on-study evaluation visit will be summarized for weight, oral temperature, sitting heart rate, respiratory rate and sitting blood pressure.

All vital sign data will be presented in by-subject data listings.

10.5. Electrocardiograms (ECGs)

Overall interpretation results for electrocardiograms (ECGs) and the investigator interpretation results are collected as normal, abnormal not clinically significant (NCS), and abnormal clinically significant (CS). Subjects whose interpretations shift from normal to abnormal (CS or NCS) will be listed separately, including description of the abnormality and any associated comments.

All ECG results will be presented in by-subject data listings.

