9.7.2.4. Every 6 Months from Month 12, ET, and Month 60 (EOS)

The following procedures will be performed as listed in [Table 3](#):

- Verify that the subject has fasted for at least 8 hours
 - Record fasting status in the source and eCRF
 - If the subject reports having drunk or eaten anything other than water within 8 hours, document accordingly in the source and eCRF and remind the subject that fasting is required before all onsite study visits
- Record concomitant medications
- Assess and record any AEs including myopathy evaluation
- Perform physical examination
- Record weight and BMI and WHR
- Record vital signs (body temperature, sitting heart rate, respiratory rate, and seated blood pressure after sitting 3 minutes)
- Perform standard 12-lead ECG only at ET and Month 60 (EOS)
- Calculations for the following:
 - CP Score/Class (assessment of ascites and hepatic encephalopathy is required). See [Section 7.4.4](#) for additional information regarding CP scoring.
 - MELD Score: to be calculated from serum chemistry and other parameters
 - MRS
 - [REDACTED]
 - GLOBE and UK-PBC scores
- Obtain blood samples for the following:
 - Serum chemistry, hematology, and coagulation; see analytes listed in [Table 11](#)

- Urinalysis
- Perform a urine-based β -hCG pregnancy test for females of childbearing potential. A female of childbearing potential is defined as fertile, following menarche and until becoming post-menopausal unless permanently sterile. Permanent sterilization methods include hysterectomy, bilateral salpingectomy and bilateral oophorectomy. A postmenopausal state is defined as no menses for 12 months without an alternative medical cause.
- TE (only if test is available at qualified sites)
- Dispense/administer investigational product (not at ET or Month 60)
- Assess investigational product accountability and compliance
- Remind subject to fast at least 8 hours prior to next visit (not at Month 60)

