14.2.5. Electrocardiogram

Standard 12-lead ECGs will be collected at the timepoints indicated in [Table 3](#). ECGs will be recorded using the site's standard ECG equipment. Collection of additional ECGs for routine safety monitoring at additional timepoints or days is at the discretion of the Investigator based on GCP.

All ECGs should be collected after at least 5 minutes of supine rest and prior to blood sample collection. Safety ECGs will be obtained using a 12-lead digital ECG recorder. The ECG will include all 12-standard leads and will be recorded at a paper speed of 25 mm/sec. Standard ECG parameters will be measured, including heart rate (HR), RR, PR, QT, QTc intervals, and QRS duration. The 12-lead ECG results will be reviewed by the Investigator or designee, and findings will be recorded in the eCRF as normal, abnormal but not CS, or abnormal and CS. Any CS abnormality on ECGs recorded after dosing should be reported as an AE.

If a subject shows an abnormal assessment at any stage, repeat measurements may be made and the abnormality followed to resolution if required. Additional measurements may be taken as deemed necessary by the Investigator.

The investigative site must retain a copy of all 12-lead ECGs evaluated by the Investigator or designee. These ECGs must be clearly labeled with the subject's initials, Subject ID number, date, and time.

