15.3. Safety Analysis

The LTSE Population will be the primary population used for safety analyses.

Safety data, including SAEs, TEAEs, physical examinations, ECGs, vital signs, clinical laboratory assessments, and treatment discontinuations, will be assessed.

The incidence of TEAEs and SAEs will be tabulated by system organ class, preferred term, and severity.

All events of potential hepatic injury, suspected liver-related clinical outcomes, and potential renal injury that occur after administration of the first dose of the investigational product will be reviewed and adjudicated by independent adjudication committees ([Section 14.3](#)).

Laboratory parameters and vital signs will be summarized (including Hy's law) using descriptive statistics at baseline (defined as the last assessment performed before the first dose of investigational product in Study 977-311) and at each scheduled post-baseline visit in Study 977-311. The change from baseline will also be summarized. ECGs will be summarized using frequency at each visit. The shift from baseline will also be summarized.

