5. GENERAL CONSIDERATION

Individual subject data obtained from electronic case report forms (eCRFs), central and local laboratories, external sources, and any derived data will be presented in data listings by subject. All data listings that contain an evaluation date will contain a relative study day. Pre-treatment and on-treatment study days are numbered relative to the day of the first dose of investigational product which is designated as Day 1. The preceding day is Day -1, the day before that is Day -2, etc. The last day of investigational product is designated with an "L" (e.g., Day 14L). Post-treatment study days are numbered relative to the last dose and are designated as Day 1P, Day 2P, etc.

Tabulations will be produced for appropriate demographic, Baseline, efficacy, and safety parameters.

For categorical variables, summary tabulations of the number and percentage of subjects within each category (with a category for missing data) of the parameter will be presented. Percentage calculations will be based on non-missing data, unless otherwise specified. Percentages are rounded to 1 decimal place, unless otherwise specified.

For continuous variables, the number of subjects, mean, standard deviation (SD), standard error of the mean (SEM), median, minimum, and maximum values will be presented. The precision of summary statistics, unless otherwise specified will be as follows: mean and median to 1 more

decimal place than the raw data, and SD and SEM to 2 decimal places more than the raw data. In general, the decimal places should not exceed 3 decimal places unless appropriate.

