11. DEVIATIONS FROM PROTOCOL

There have been no deviations between the protocol-defined statistical analyses and those presented in this statistical analysis plan.

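### SAP 10.5 leaves worsening from abnormal NCS to abnormal CS out of its ECG shift listing and does not specify the ECG shift summary promised in the protocol, while SAP 11 declares no deviations

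*SAP*

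**What the plan says.** Protocol 15.3 names ECGs among the safety data and commits to two summaries: "ECGs will be summarized using frequency at each visit. The shift from baseline will also be summarized". Protocol 15.3.2 and the Synopsis repeat the commitment.

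SAP 10.5 describes three interpretation categories (normal, abnormal NCS, abnormal CS) and two outputs, both listings. The first is selective: "Subjects whose interpretations shift from normal to abnormal (CS or NCS) will be listed separately". The second is complete: "All ECG results will be presented in by-subject data listings". The section names no table.

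SAP 11 then states: "There have been no deviations between the protocol-defined statistical analyses and those presented in this statistical analysis plan".

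Two other places bear on the point. Protocol 14.2.5 says: "Any CS abnormality on ECGs recorded after dosing should be reported as an AE". SAP 5 has a general sentence: "Tabulations will be produced for appropriate demographic, Baseline, efficacy, and safety parameters".

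**The concern.** There are two separate defects.

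First, the selective listing is defined by where the subject starts. A subject must have a normal baseline ECG to appear in it. Someone who starts at NCS and ends at CS has worsened to a clinically significant finding but does not meet the definition.

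Second, a listing is not a summary. It carries no counts, percentages or denominators, so it does not deliver the shift-from-baseline summary in the protocol. SAP 11 tells the reader that nothing has changed.

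The study's primary objective is long-term safety and tolerability. Protocol Table 3 schedules ECGs only at Day 1, early termination (ET) and Month 60, so the planned ECG evidence is essentially one comparison per subject, baseline against end. That comparison is the one with no specified summary.

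**Working it through.** The plan gives no figure to reproduce. The check is a comparison of texts and a count of transitions.

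**1. Transitions.** Three categories at baseline by three after baseline give 3 x 3 = 9 cells: 3 unchanged, 3 improving and 3 worsening. Applying the SAP 10.5 rule to the worsening cells:

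| Baseline | Post-baseline | In the SAP 10.5 shift listing? |
|---|---|---|
| Normal | Abnormal NCS | Yes |
| Normal | Abnormal CS | Yes |
| Abnormal NCS | Abnormal CS | No |

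The rule captures 2 of 3. The omitted cell can be occupied, because exclusion criterion 12 bars clinically concerning arrhythmias and prolonged QT/QTc but not every minor abnormality.

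**2. Protocol summaries carried into SAP 10.5.** The protocol promises two, frequency by visit and shift from baseline. SAP 10.5 names 0 of 2.

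**3. Comparison within the SAP.** SAP 10.3 sets out 3-by-3 laboratory shift tables. The Child-Pugh section specifies shift tables for class. SAP 10.4 and 10.6, on either side of the ECG section, each state a summary by visit. SAP 10.5 states none.

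**4. Whether the adverse event outputs fill the gap.**
- A CS abnormality after dosing should become an AE under protocol 14.2.5, so it should appear in the all-AE listing.
- SAP 10.2.3 restricts AE summaries to TEAEs, and SAP 10.2.1 excludes events starting more than 30 days after the last dose. Protocol 7.6 and 8.4 ask subjects who stop treatment to keep attending until Month 60. If such a subject's first CS finding comes at a Month 60 ECG more than 30 days after the last dose, it is outside every TEAE table.
- The specified AE tables by system organ class and preferred term show neither the baseline ECG category nor how many subjects had a post-baseline ECG.
- A shift from normal to NCS need not produce an AE, so only an ECG table would count it.

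**5. After the fix.** With the listing rule set to any move to a worse category, 3 of 3 worsening cells are captured. With the two tables added, 2 of 2 protocol summaries are present.

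**The case against.** The strongest reply is that little is lost. All ECG results are listed, CS findings after dosing have a reporting route as AEs, and most subjects will have one scheduled post-baseline ECG, so worsening could be counted from the listing. The study is single-arm and tests no hypothesis. That stands as a limit on importance.

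A reader might go further and infer that NCS-to-CS worsening would never be flagged anywhere. The documents do not support this. The AE route and the full ECG listing both remain, and the omission belongs to the ECG shift listing. Nor does that listing catch only trivial change, since it explicitly includes normal to CS.

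A reader might also infer that both protocol summaries were deliberately removed. SAP 1 describes the SAP as adding detail to the protocol's analyses, and where the SAP intends no summary it can say so, as SAP 10.3 does for urinalysis. The general sentence in SAP 5 could be read to cover an ECG frequency table. For frequencies, therefore, the fair statement is that SAP 10.5 does not explicitly specify them. The sentence does not supply a shift summary, which this SAP spells out elsewhere when it wants one.

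Finally, a reader might want to put a number on the subjects affected. The documents give no distribution of baseline ECG categories. Any assumed share of NCS baselines would count subjects in a starting category, not subjects who worsened, and the number of NCS-to-CS shifts could be zero.

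**Conclusion.** The point holds in limited form. The ECG shift listing omits one of three worsening transitions, the one from NCS to CS. The protocol's shift-from-baseline summary is not specified in the SAP, the frequency summary is not explicit, and the statement in SAP 11 is therefore inaccurate on ECGs.

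The practical size is modest: one baseline-to-end comparison, with the underlying data still visible in listings and CS findings expected in the AE data. What is missing is a specified count of worsening by baseline category with a denominator, and TEAE-table coverage of CS findings that start more than 30 days after the last dose. The conclusion assumes that SAP 10.5 is applied as written and that the sentence in SAP 5 is not taken to imply a shift table. It does not depend on any assumed prevalence of abnormal baseline ECGs.

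**What to change.** In SAP 10.5:

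- Add a frequency table of normal, NCS and CS at each scheduled ECG visit (Day 1, ET, Month 60), with the number of subjects who have an ECG as the denominator.
- Add a 3x3 shift table from baseline to the post-baseline ECG (ET or Month 60).
- Redefine the selective listing as any shift to a worse category, including NCS to CS.

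If the sponsor prefers not to produce the summaries, SAP 11 should declare the departure and give the reason. A separate worst-post-baseline analysis is not needed: the protocol does not ask for one, and with so few scheduled ECGs it would add almost nothing.

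The cost is two standard tables and a one-line change to a listing rule. The interpretations are already recorded on the eCRF, so no new data are needed.

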10.6. Physical Exam

The results of physical exam will be summarized by visit.

All physical exam data will be presented in by-subject data listings.

10.7. Prior and Concomitant Medications

Prior medications are those medications with start and stop prior to the initial dose of investigational product. Concomitant medications are those medications started prior and continued after the initial dose of investigational product were. If it cannot be determined whether the medication was a concomitant medication due to a partial start or stop date or if the medication is taken on the same date as the initial dose of investigational product, then it will be counted as a concomitant medication.

Prior medications will be listed only. Concomitant medications will be summarized by World Health Organization (WHO) Anatomical Therapeutic Chemical (ATC) class level 2, WHO ATC class level 4 and preferred name using the LTSE Population. These summaries will present the number and percentage of subjects using each medication. Subjects may have more than one medication per ATC class and preferred name. At each level of subject summarization, a subject is counted once if he/she reported one or more medications at that level. Each summary will be ordered by descending order of incidence of ATC class and preferred name within each ATC class.

10.8. Subgroup Analyses of Safety

No subgroup analysis of safety is planned in this study.

11. DEVIATIONS FROM PROTOCOL

There have been no deviations between the protocol-defined statistical analyses and those presented in this statistical analysis plan.

APPENDIX A. DATA PRESENTATION CONVENTIONS:

Unless otherwise specified, the baseline value for analyses of all parameters is defined as the last non-missing value prior to the first administration of investigational product.

For categorical variables, the number and percentage of subjects within each category of the parameter, including a category for missing data, will be presented. Percentage calculations will be based on the analysis population, unless otherwise specified.

For continuous variables, summary statistics will include the number of subjects and the mean, standard deviation (SD), standard error of the mean (SEM), median, 25th and 75th quartiles, minimum, and maximum values.

All statistical analyses will be performed using SAS statistical software Version 9.4 or higher unless otherwise noted.
